Assumptions for blood pressure treatments

Annual endpoint-rate (%) in the control group unadjusted for losses, crossover and statin-effect	2.00
Relative effect of "contemporary" compared with "standard" BP-treatment (per protocol) (%)	20
Relative effect of BP-treatment corrected for losses and crossover Intention to Treat (ITT) %	15-16
Proportion statin treated open or randomised (%)	40-45
Treatment effect in endpoint rate by statin (ITT) 10 mg atorvastatin (%)	30
Relative reduction (%) in endpoint rate in the "blood pressure standard" group because of statin treatment effect (%)	18
Cumulative losses of endpoint during 5 year (%)	10
Cumulative cross-over from "standard" to "contemporary" (%)	20
Cumulative cross-over from "contemporary" to "standard" (%)	20
Annual endpoint-rate (%) in the "standard" BP treatment group after adjustment for #	1.42
Cumulative endpoint rate (%) during 5 years in the control group after adjustment for #	6.9
Significance level (alpha) (%) Interim analysis by safety committee will use level 0.005 leaving 0.045 for final test	5
Sample size (9000 contemporary + 9000 standard)	18000
Power (%)	80 ← lower power

losses and the dilution effect from cross-over and statin effect

b. Comparison of atorvastatin and placebo

These calculations are based on the experience from clinical trials and epidemiological data.^{9-19,28,29} It is assumed that 9000 patients (50%) will be randomised to either 10 mg atorvastatin or placebo (see section III C).

The following assumptions are made:

Cholesterol reduction with 10 mg atorvastatin (%)	30
Difference in cholesterol between 10 mg atorvastatin and placebo (mmol/l) 1.7	
Relative (%) effect on endpoint (nonfatal MI and fatal CHD) of 10 mg atorvastatin compared with placebo (40% optimally in long term studies) (ITT)	30
Power for the primary endpoint (nonfatal MI and fatal CHD) given by Cumulative endpoint rate (nonfatal MI and fatal CHD) on placebo for five years (%)	6.35
Significance level (%)	1
Sample size	9000
Power (%)	90

2. Statistical analysis

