The statistical method for the main analysis will be a log rank test using time to event (nonfatal MI and fatal CHD) as the primary information. The significance level for the primary comparisons of the antihypertensive and the lipid lowering components will be 0.05, both including adjustment for interim looks (for details see section V E.1) and 0.01 for secondary and tertiary analyses. These analyses will be done without adjusting for baseline factors and will be performed according to the intention to treat principles (ITT). All analyses using 'time to particular event' will be analysed in the same way. The Cox proportional hazards model with adjustment for important prognostic variables will be done as complementary analyses.

Analyses using information on compliance with treatment (per protocol analyses) will be done as secondary analyses. To some extent these analyses are more sensitive to the rate of cross-over or discontinuation.

Main effect variables will also be analysed in certain subgroups to search for possible interactions. Such analyses will be seen as explanatory, will involve chi-square tests for interaction, and will be foundations for future hypotheses. P-values and confidence intervals will be presented for all comparisons.

The statistical analyses will be performed by the two co-ordinating centres under the supervision of the ASCOT Steering Committee. The unblinded statistical information for the Safety Committee will be provided by one specially named person at the co-ordinating centre in Gothenburg.

V F Disclosure of data and publication

All information obtained as a result of the study will be regarded as CONFIDENTIAL, at least until appropriate analysis and review by the Sponsors and investigator(s) are completed. Permission from the Executive Committee is necessary prior to disclosing any information relative to this study outside of the Steering Committee. It is proposed that the results relating to the two primary endpoints will be published separately. The results may be published or presented by the investigator(s), but the major Sponsors (Pfizer) will be provided with a complete dataset. All sponsors (Pfizer, Servier, and Lovens) will be given the opportunity to review and comment on any such results for up to 1 month before any presentations or publications are produced.

V I INVESTIGATOR'S APPROVAL

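### The atorvastatin–placebo primary comparison is sized at a 1% significance level but tested at 0.05, so the stated 90% power does not describe the planned test, and its final-look level is not clearly fixed

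*Protocol*

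**What the plan says.** Protocol section V E 2 specifies the analysis: "The statistical method for the main analysis will be a log rank test using time to event (nonfatal MI and fatal CHD") is the endpoint definition and method for the main analysis. It then fixes the level: "The significance level for the primary comparisons of the antihypertensive and the lipid lowering components will be 0.05, both including adjustment for interim looks". The sentence continues with a cross-reference and a stricter level for the lower-ranked endpoints: "for details see section V E.1) and 0.01 for secondary and tertiary analyses".

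Section V E 1 b sizes the atorvastatin–placebo comparison. Its entries are introduced by "The following assumptions are made" and include "Cumulative endpoint rate (nonfatal MI and fatal CHD) on placebo for five years (%) 6.35", a 30% relative effect by intention to treat, "Significance level (%) 1", a sample size of 9000 and power of 90%. It gives no interim level and no final level.

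Section V E 1 a sizes the blood-pressure comparison. Its significance row says 5% and adds the operating rule: "Interim analysis by safety committee will use level 0.005 leaving 0.045 for final test". This is the only interim split in V E 1.

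**The concern.** The significance level of a primary comparison is its success criterion. Here one comparison carries 1% in one section and 0.05 in the next, and the protocol does not say how they relate. Two things are at stake.

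- **The power statement.** If the 90% was computed at 1%, it is not the power of the test that V E 2 prescribes.
- **The final-look level.** V E 2 says the lipid level already allows for interim looks and points to V E 1 for the details. A reader who follows that pointer to the lipid table finds a different level and no split. In the blood-pressure table the corresponding row does carry the operating test level, so it is natural, though not compelled, to read the lipid row the same way.

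This limb also appears to have ended early. Section IV B 4 j says that one arm has been discontinued before the other, and section IV C refers to discontinuation of the lipid-lowering arm. The protocol does not say why. A reader would want to know which boundaries applied.

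**Working it through.** **Inputs.** From V E 1 b: placebo five-year rate 6.35%, relative reduction 30%, 9000 patients, level 1%, power 90%. From Table 3 in III C: 4500 per group. From V E 2: log-rank test, level 0.05. From V E 1 a: split 0.005 / 0.045. Assumptions: two-sided testing (not stated) and a hazard ratio of 0.70 for the 30% reduction.

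**Step 1: expected events.** The atorvastatin rate is 0.70 × 6.35% = 4.445%. Events = 4500 × (0.0635 + 0.04445) = 485.8, about 486.

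**Step 2: reproduce the plan's 90%.** With Schoenfeld's formula for the log-rank test, power = Φ(|ln HR| × √(events/4) − z). The signal is 0.3567 × √(485.8/4) = 0.3567 × 11.02 = 3.931.

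| Two-sided level | z | Power |
|---|---|---|
| 0.01 | 2.576 | Φ(1.355) = 91.2% |
| 0.045 | 2.005 | Φ(1.926) = 97.3% |
| 0.05 | 1.960 | Φ(1.971) = 97.6% |

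Other conventions agree. If the atorvastatin rate comes from proportional hazards, 1 − (1 − 0.0635)^0.7 = 4.49%, two-sided 1% gives 91.4% by log-rank and 90.7% by two proportions. Two proportions with 4.445% gives 92.3%. Across these methods, two-sided 5% gives 97.4% to 97.9%. One-sided 1% gives 94.6% by log-rank and 95.3% by two proportions, further from the stated figure. The stated 90% is therefore a two-sided 1% calculation, and the 1% is not a misprint for 5%.

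**Step 3: what 5% would have required.** By two proportions (6.35% against 4.445%), 90% power at two-sided 5% needs 2955 per group, or 2 × 2955 = 5910 in total. At 1% it needs 4185 per group, or 8370, which is close to the planned 9000.

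**Step 4: how far apart the thresholds are.** The critical hazard ratio is exp(−z / 11.02).

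- At 0.01: 0.792, an observed reduction of 20.8%.
- At 0.045: 0.834, a reduction of 16.6%.
- At 0.05: 0.837, a reduction of 16.3%.

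Under the design effect, the chance of a result significant at 5% but not at 1% is 97.6 − 91.2 = 6.4 points. If the true reduction were 20%, it would be 73.7 − 50.8 = 22.9 points (two proportions). The band between 0.045 and 0.05 is far narrower: 97.6 − 97.3 = 0.3 points under the design effect.

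**The case against.** The best defence is that V E 2 settles the matter. It is the section that fixes the test, it names the lipid comparison, and it reserves 0.01 for secondary and tertiary analyses. The 1% is listed as a sizing assumption beside the expected cholesterol reduction and event rate. Sizing at a stricter level than is tested is conservative: power rises and type I error is untouched. On the interim, V E 2 cites V E 1 as a whole, so the single split there can be read as applying to both comparisons, and fuller detail may be in a statistical analysis plan that is not shown.

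Most of this stands, and it rules out three stronger readings.

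- A reader might infer that a p-value between 0.01 and 0.05 has no defined verdict. V E 2 does define it: p = 0.03 is significant.
- A reader might infer inflated type I error. Nothing in V E 2 as written supports that.
- A reader might take the blood-pressure table's 0.005 out of a 1% lipid allowance and conclude that final power falls below 90%. No section prescribes that split.

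What the defence does not remove is that the protocol never says the 1% is for sizing only, that the printed power belongs to a test V E 2 does not prescribe, and that the pointer to V E 1 leads to no interim or final level in the lipid table.

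**Conclusion.** The inconsistency is real but limited. V E 1 b and V E 2 give different levels for the same primary comparison without reconciling them. The stated 90% power reproduces at two-sided 1% (about 91%) and understates the power of the test in V E 2, which is about 97.6% at 0.05 or 97.3% at 0.045. On V E 2 as written, the only uncertain range for the decision is p from about 0.045 to 0.05, because the lipid split is not stated. These figures rest on two-sided testing, 4500 per group, the tabulated event rate and a hazard ratio of 0.70.

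That 1% reproduces the 90% is no reason to tighten V E 2. Exceeding the planned power is not a fault, and this version already refers to the lipid arm as discontinued, so altering its threshold now would come after its treatment phase had ended.

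**What to change.** Make V E 1 b agree with V E 2:

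1. Change the lipid significance row to 5%, or keep 1% and label it as a sizing value only.
2. Restate power as about 97% at the tested level, and state the sidedness.
3. Give the interim and final levels for the lipid comparison in V E 1 b, so that the cross-reference from V E 2 leads somewhere. If the 0.005 / 0.045 split was meant for both comparisons, say so.

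If records from before any unblinded look show that 1% was the pre-specified test level, document that, correct V E 2 instead, and state how the 1% is divided between looks. That route makes the success criterion stricter, so it should rest on such records alone.

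The cost is protocol wording. Sample size, conduct and data collection do not change, and on the main route neither does the overall 0.05 level in V E 2.

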APPENDIX IA

Intermittent Claudication Questionnaire

PATIENT DETAILS

Affix label here (Name, Address, DOB & Study No)

VISIT NUMBER

--	--

DATE

day		month		year	

1. Do you get pain or discomfort in you leg(s) when you walk?

Yes

No

I am unable to walk

If you answered "YES" to question 1 – please answer the following questions. Otherwise you need not continue.

2. Does this pain ever begin when you are standing still or sitting?

Yes No

3. Do you get it if you walk uphill or hurry?

Yes No

4. Do you get it when you walk at an ordinary pace on the level?

Yes No

[figure not shown]
5. What happens to it if you stand still?

Usually continues more than 10 minutes

[figure not shown]
Usually disappears in 10 minutes or less

6. Where do you get this pain or discomfort?
Mark the place(s) with "X" on the diagram below.

Front

Back

SCORING THE INTERMITTENT CLAUDICATION QUESTIONNAIRE

A classification of definite claudication requires all the following responses:

- Question 1 - Yes
- Question 2 - No
- Question 3 - Yes
- Question 5 - Usually disappears in 10 minutes or less
- Question 6 - Pain clearly indicated within the calf muscle, regardless of whether pain is also marked in other sites

A classification of atypical claudication requires all the following responses:

- Question 1-5 - as above
- Question 6 - Pain indicated in the thigh or buttock, in the absence of any calf pain

Grading degree of claudication

- Question 4 - Yes = Grade 2
- No = Grade 1

Sites excluding claudication

A diagnosis of intermittent claudication should be excluded if pain is indicated in the hamstrings, feet, shins, joints, or appears to radiate, in the absence of any pain in the calf.

APPENDIX IB

Diabetes criteria

WHO criteria for the diagnosis of diabetes in patients with symptoms are:

- a fasting venous plasma glucose concentration of 7mmol/l or more (confirmed on a second measurement) or a 2-hour value of 11.1mmol/l or more following a 75g load.

If the 2-hour value is in the range 7-11 mmol/l the diagnosis is impaired glucose tolerance. Glucose tolerance tests should be performed in all those whose fasting concentration is in the range 6-6.9mmol/l: a fasting concentration of less than 6mmol/l excludes the diagnosis.

Patients who have been diagnosed as having non-insulin dependent diabetes (NIDDM) in the past but who are controlled with a special diet will also be considered as having NIDDM for the purposes of the study.

Subjects currently treated with insulin with a history of onset of diabetes after the age of 40, and body weight in excess of ideal body weight at the time of diagnosis, and treated with oral agents for a period of two years will also be considered to have NIDDM.

APPENDIX IC

BLOOD PRESSURE MEASUREMENT

Responsibilities

Research nurses/Investigators trained in the method are responsible for measuring and recording digital blood pressures from patients.

Equipment

- Digital blood pressure monitor (Omron HEM-705CP with modifications requested for ASCOT))
- Blood pressure cuffs (1 regular and 1 large)
- Rechargeable batteries (R14C)
- Printer paper
- Tape measure

Method

OMRON HEM 705-CP has fulfilled the requirements for accuracy of the protocols of the Association for the Advancement of Medical Instrumentation (AAMI) and the British Hypertension Society (BHS). Moreover the device provides hard copy of the blood pressure measurements and pulse rate together with the time and date of recording

Instructions for using the OMRON HEM 705-CP

Before use

- The nurse/investigator must read the accompanying instruction manual carefully, insert batteries and print paper, and then familiarise him/herself by using the device on one or more volunteers. A step-by-step instruction card as a guide for day-to-day use will be provided with each device.
- Set the time and date.

General Information

- The device should be calibrated at 1 year (\pm 2 months) intervals by the monitor with the reference equipment supplied.
- Batteries should be replaced when the symbol indicating low battery power is shown. Batteries should provide for 500 measurements.
- The nurse/Investigator should ideally be the same for each individual patient throughout the study. Where this is not possible every effort should be made to

ensure that a consistent type of observer (nurse or doctor) measures blood pressure for each individual throughout the study.

Preparation of patient

- Ensure that the patient is as relaxed as possible with an empty bladder. Instruct the patient to sit with both feet parallel and flat on the floor.
- Ensure that the patients have neither smoked nor consumed alcohol in the 30 minutes before blood pressure measurement.
- Patients should rest for 5 minutes in the sitting position before measurement.
- Patients should not talk during blood pressure measurement.

The cuff

- Arm circumference (AC) should be measured midway between the shoulder tip and the olecranon process.
- If AC <32cm use standard cuff; if AC \geq 32cm use large cuff. If arm circumference <24cm use the standard cuff adjusting the velcro strip as illustrated in the OMRON manual page 6 section 4.

Cuff sizes

Arm Circumference	Cuff
24 – 32cm	Standard
32 – 42cm	Large

- The cuffs are designed for blood pressure measurement on the left arm. If the cuff cannot be applied on the left arm, the right arm can be used – but be certain that the green strip on the lower boundary of the cuff is always on the brachial artery. The same arm should be used throughout the study.
- The cuff can be placed over a shirt or blouse sleeve.
- See Omron manual (pages 6,7)for correct placement of cuff.
- Ensure that the arm is supported on a cushion or table top, so the cuff position is in line with the level of their heart (see the manual illustration).
- Instruct the patient to relax and take 5-6 deep breaths prior to commencing the procedure. This aids in stabilising their blood pressure.

Preparation of equipment and taking the blood pressure

- Insert the air inflation tubing plug from the cuff into the air jack of the monitor. Switch on the device by pressing the SPHYG/CLOCK button, and wait until the display shows a '0'.
- Select range of blood pressure with the PRESSURE VALVE PRESET switch on the AUTO mode the cuff inflates to about 170mmHg. If pressures above this level are anticipated put the switch to 240. If the measurement fails, 'EE' will show and if in the AUTO mode, try again with position 240.
- Press the START (inflation) button and immediately release it. A noise will sound and the monitor automatically commences. The screen will flash a heart symbol during the process.
- A sound will indicate the recording has taken place. The cuff then deflates and the BP and pulse will be displayed in the screen. There is a latent period of 3.5 seconds for the BP to be displayed and a further 2 seconds for the pulse.
- If any of the error codes – 'E' – are displayed, refer to page 19 of the instruction manual and after rectifying the source of error, repeat measurement.

Printing the Data

- Press PRINT CURRENT READING button and print-out will give the date and time of measurement, systolic and diastolic pressure and pulse rate.
- After about 1 minute repeat measurement.
- Press PRINT CURRENT READING button
- After about 1 minute repeat measurement.
- Press PRINT CURRENT READING button.
- Calculate the mean of the second and third readings. In the UK the database will automatically calculate the mean. In Scandinavia calculate the mean by adding the two measurements together and divide by two.
- Detach print out, write the date and patient's ID on the front of the print out and attach it to a blood pressure log form (Appendix 1)(with adhesive).
- Take a copy and add the original and the copy to the worksheet/central file.
- Record the last three readings on the CRF.
- Enter the mean of the last two readings on the worksheet. This mean will be used in the analyses.

Additional Information

- Cuff inflation can be terminated by pressing the SPHYG/CLOCK button.
- For insufficient inflation pressure settings, the cuff will automatically re-pressurise to a pressure 40mmHg higher than the previous inflation pressure.
- Do not clean the monitor with detergents; if dirty, wipe with a damp cloth.

Problems

- If you cannot obtain a blood pressure recording with the OMRON HEM-705 CP: a recording should be made using a conventional sphygmomanometer. The measurement should be written into the CRF with an explanatory note.
- If the OMRON HEM 705-CP fails to function: contact the co-ordinating centre, which will provide a replacement device.
- The OMRON will be calibrated at yearly intervals by the Study Monitor. If you have reason to believe that extra calibration is necessary please contact the co ordinating centre.

References

5. O'Brien E. Will mercury manometers soon be obsolete? *J Human Hypertens* 1995;9:933-934.
6. O'Brien E. Ave Atque vale. The centenary of clinical sphygmomanometry. *Lancet* 1996;348:1569-1570.

APPENDIX ID

SILENT MYOCARDIAL INFARCTION: ECG CODING

Aim

This procedure will identify patients with silent myocardial infarcts as part of the primary endpoint of the study.

The primary aim is to identify patients with newly developed ECG signs of silent myocardial infarction, ie appearance of major Q or QS items during the course of the study.

Appearance of major Q and QS items

The ECG diagnosis of major Q or QS items is based on the appearance of any of Minnesota codes in group 1.1 and 1.2 under the provision that such a code is not present in the same set of leads in the immediately preceding ECG. All ECG's with positive codes 1.1 or 1.2 at conclusion of the study are checked against the original inclusion ECG tracing. According to the specifications of the Minnesota code, a number of pre-evaluation codes are checked for possible suppression of codes 1.1 and 1.2 (see further coding protocol for details).

Silent myocardial infarction is diagnosed when there is appearance of new major Q or QS items without clinical signs of myocardial infarction.

ST segment or T-wave items and intraventricular conduction defects

ST segment changes are diagnosed when any of Minnesota codes 4.1 and 4.2 are present, T-wave changes are diagnosed when any of Minnesota codes 5.1 and 5.2 are present and intraventricular conduction defects are diagnosed when any of codes 7.1, 7.3 and 7.6 are present.

[figure not shown]
Criteria for sub-group analysis has to be decided by the Steering Committee. Patients could be classified as having possible myocardial ischemia when positive ST segment (codes 4.1 and 4.2) or T-wave (codes 5.1 and 5.2) are present or appear. In addition intraventricular conduction defects (codes 7.1, 7.3 and 7.6) may indicate IHD.

Coding procedure

ECG's are read and coded blindly according to the 'Minnesota code 1982' classification at the Clinical Experimental Research Laboratory, Department of Medicine, Sahlgrenska University Hospital/Östra (ECG Core Centre). Responsible investigator and head of the ECG Core Centre is Associate [name] MD.

In a second step, serial ECGs with new Q or QS codes are visually compared by two independent coders to determine whether the Q/QS items are definitely new or not.

ECG FLOW

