13. To compare the effects of 10mg atorvastatin with placebo on non-fatal MI, fatal CHD, non-fatal and fatal heart failure and the development of angina (total coronary endpoints).
14. To compare the effects of 10mg atorvastatin with placebo on all cardiovascular events and procedures.

II C Tertiary

1. To compare the effects of the two antihypertensive regimens and the effects of active lipid-lowering versus placebo on the development of each of the following:
 - (a) silent MI
 - (b) unstable angina
 - (c) chronic stable angina
 - (d) peripheral arterial disease
 - (e) life-threatening arrhythmias
2. To compare the effects of the two antihypertensive regimens and the effects of active lipid lowering versus placebo on the development of diabetes mellitus or renal impairment.
3. To evaluate whether synergistic effects on the study primary endpoint or cardiovascular events and procedures are observed in association with the use of atorvastatin and amlodipine.
4. To compare the effects of the different antihypertensive and lipid-lowering regimens on health care costs.
5. To compare the effect of the different antihypertensive regimes on all major study endpoints among specific sub-groups of patients (e.g. diabetics, smokers, the obese [$>30\text{Kg/m}^2$], those with LVH, older/younger [$\leq 60/>60$ years], male/female, any previous vascular disease [by history or ECG], renal dysfunction [by serum creatinine, urinalysis], with and without metabolic syndrome*).
6. To compare the effects of 10mg atorvastatin with placebo on all major study endpoints among specific subgroups of patients (e.g. diabetics, smokers, the obese [$>30\text{Kg/m}^2$], those with LVH, older/younger [$\leq 60/>60$ years], male/female, any previous vascular disease [by history or ECG], renal dysfunction [by serum creatinine, and urinalysis], with and without metabolic syndrome*).

* As defined according to NCEP III except for replacing waist-hip ratio with BMI>30 as patients with triglycerides ≥ 1.69 mmol/l, HDL-C for males <1.03 mmol/l, for women <1.29 mmol/l, BP $\geq 130/85$ mmHg, fasting glucose ≥ 6.1 mmol/l.

III STUDY DESCRIPTION

III A Design

[figure not shown]
2x2 factorial trial: The two antihypertensive regimens will be compared in a trial using the Prospective Randomised Open Blinded Endpoints (PROBE) design and 10mg atorvastatin will be compared in a double-blinded randomised trial with placebo.

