randomised. In the UK those doctors who wish to treat their patient with lipid lowering therapy (statin or fibrate) should inform the relevant study centre before randomisation. Any subjects who wish to drop out for any reason during this early run-in period will be encouraged not to continue in the study. Subjects will be randomised only if, at the end of the run-in, they seem likely to comply with the trial protocol for several more years. By this process it is anticipated that many potential drop-outs will be excluded before becoming part of the randomised comparison, with a consequent improvement in statistical sensitivity.

- Subjects whose triglyceride level was $>4.5\text{mmol/l}$ or glucose was $>7.0\text{mmol/l}$ at screening will be recalled during this period for a fasting blood sample to evaluate eligibility (see sections IV A1 and IV A3).

c. Randomisation visit (0 months)

- Physical examination.
- BP and HR.
- Fasting blood sample: total cholesterol, HDL, triglycerides, and glucose.
- 12 lead ECG (to be posted to ASCOT Scandinavian Co-ordinating Centre, Gothenburg University Clinical Research Institute, [name], Sweden).
- Eligibility and consent confirmed.
- Randomisation allocated using minimisation procedures by the appropriate co-ordinating centre by telephone.
- All previous antihypertensive medication withdrawn. Continue and record all other existing medication.
- Study medication allocated (see section IV B3).
- Appointment made for next visit.
- Adverse events (including hospitalisation, diagnosis, duration) recorded.

d. First follow-up visit (6 ± 2 weeks)

- Endpoints recorded.
- Adverse events (including hospitalization, diagnosis, duration) recorded.
- BP and HR.
- Non-fasting blood sample for electrolytes and creatinine, if started on an ACE inhibitor at 0 months. (This test is required within a few weeks of initiating an ACE inhibitor at any point in the trial).
- BP treatment modified if BP above target (see section IV B3).
- Changes in medication recorded.
- Study medication allocated.
- Appointment made for next visit.

e. Second follow-up visit (3±1 months)

- Endpoints recorded.
- Adverse events recorded.
- BP and HR.
- BP treatment modified if BP above target (see section IV B3).
- Changes in medication recorded.
- Study medication allocated.
- Appointment made for next visit.

f. Third follow-up visit (6±1 month)

- Endpoints recorded.
- Adverse events recorded.
- BP and HR.

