- Fasting blood sample: total cholesterol, HDL, triglycerides, glucose, electrolytes, creatinine and, if randomised to statin/placebo, liver function tests (LFT's).
- Urine: stix for protein, blood and sugar.
- BP treatment modified if BP above target (see section IV B3).
- Changes in medication recorded.
- Study medication allocated.
- Appointment made for next visit.

g. Subsequent follow-up visit (year 1, 2, 3, 4, 5 ± 1 month)

- Body weight.
- Endpoints and adverse events recorded.
- BP and HR.
- ECG at year 2 only.
- Fasting blood sample: Hb, total cholesterol, HDL, triglycerides, glucose, electrolytes, creatinine, liver function tests (LFT's), and at year 2 only extra blood for frozen storage.
- Urine: stix for protein, blood and sugar.
- BP treatment modified if BP above target (see section IV B3).
- Changes in medication recorded.
- Study medication allocated.
- Appointment made for next visit.

h. Follow-up visit (years 1½, 2½, 3½, 4½, 5½ ± 1 month)

- Endpoints and adverse events recorded.
- BP and HR.
- Smoking and alcohol intake recorded.
- BP treatment modified if BP above target (see section IV B3).
- Study medication allocated.
- Appointment made for next visit.

i. Extra visits

In addition it may be necessary to arrange extra visits to control or monitor blood pressure or for other reasons. The timing of all visits and any extra visits should be recorded in the case record forms, including the reason for the visit and any extra laboratory tests or procedures carried out.

j. Final visit

All participating subjects should have a final assessment at the end of the study. This assessment should include:

- Endpoints and adverse events recorded.
- BP and HR.
- Body weight measurements.
- Smoking and alcohol intake recorded.
- ECG.
- Fasting blood sample for lipid profile; HB, glucose, creatinine, electrolytes and liver function tests (LFT's), and extra blood for frozen storage.
- Urinalysis with stix for microalbuminuria, protein, blood and sugar.
- Changes in medication recorded.

As one arm of the trial has been discontinued before the other, a final visit examination will be performed for the patients involved in the discontinued arm of the trial. These patients will then continue in the remaining arm of the trial until the study is finally terminated, when a final visit for that limb of the trial will also be carried out.

k. SUMMARY SCHEDULE OF EVENTS

1 2 3 4 5 6 7 8 9

MONTHS	-1	0	1.5	3	6	12	18	24	30	36	42	48	54	60†	66/ final

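### The one candidate rule offered for an ECG ischaemia subgroup would admit ST-T codes that develop after randomisation; if adopted, the subgroup comparison would not be randomised and could be biased

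*Protocol*

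**What the plan says.** Protocol Appendix ID, in the part on ST segment, T-wave and conduction items, states: "Criteria for sub-group analysis has to be decided by the Steering Committee". The next sentence says that patients could be classed as having possible myocardial ischaemia "when positive ST segment (codes 4.1 and 4.2) or T-wave (codes 5.1 and 5.2) are present or appear". It then adds that conduction defects (codes 7.1, 7.3 and 7.6) may also point to ischaemic heart disease. No other criterion is offered.

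The same appendix shows what appearance means there. Its main aim is to find new infarction signs, "ie appearance of major Q or QS items during the course of the study", judged against the preceding tracing. It also says of the serial ECG reading: "This procedure will identify patients with silent myocardial infarcts as part of the primary endpoint of the study".

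Section IV B 4 gives the timing. An ECG is taken at the randomisation visit: "12 lead ECG (to be posted to ASCOT Scandinavian Co-ordinating Centre". The annual-visit list has "ECG at year 2 only", and the final visit has another ECG.

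Section II C, tertiary objectives 5 and 6, gives examples of subgroups, among them "any previous vascular disease [by history or ECG" (the bracket also closes there). The ST-T class is not among the examples. Section V E 2 says of subgroup work: "Such analyses will be seen as explanatory, will involve chi-square tests for interaction, and will be foundations for future hypotheses".

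**The concern.** The candidate sets codes that are present against codes that appear. Given how the appendix uses appearance, the second limb brings in patients whose ST-T codes arise after randomisation. Nothing in Appendix ID, section II C or section V E 2 limits this class to the baseline tracing.

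Membership could then depend on what happens during treatment, in three ways:

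- A regimen may change how often ST-T codes develop.
- An infarction can leave ST-T codes on the next ECG, so having the endpoint can bring a patient into the subgroup.
- A patient who dies before the next scheduled ECG cannot acquire a code and is left outside.

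At stake are the subgroup treatment ratio and the interaction test. Section V E 2 promises P-values and confidence intervals for all comparisons and treats subgroup results as a base for later hypotheses. An interaction produced by the membership rule would be passed on as a lead.

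**Working it through.** **What can be reproduced.** No figure in the protocol depends on this class. Two planning figures serve as inputs. The 5-year control endpoint rate is 6.9%, which follows from the adjusted annual rate of 1.42%: 1 − (1 − 0.0142)^5 = 0.069. The intention-to-treat effect is 15-16%, midpoint ratio 0.845 (both section V E 1). The protocol gives no ECG code rates, so all of those below are assumptions.

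**Notation.** p = share with ST-T codes at baseline; q = chance that an event leaves a new code; n = chance of a new background code in control; r = ratio by which treatment multiplies n. Neither calculation models death before the next ECG.

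**Calculation 1: no true effect on MI.** Assume p = 0.15, n = 0.10 and q = 0.30 or 0.60. The MI rate is 1.25% per year without baseline codes and 1.8 times that (2.25%) with them. The average is 0.85 × 1.25 + 0.15 × 2.25 = 1.40% per year, close to the protocol's 1.42%. Five-year risks are R0 = 1 − exp(−0.0625) = 0.0606 and R1 = 1 − exp(−0.1125) = 0.1064. A patient with an event is coded through the event or the background: q* = 1 − (1 − q)(1 − nr).

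- Subgroup share = p + (1 − p)[R0 q* + (1 − R0) nr]
- Subgroup events = p R1 + (1 − p) R0 q*

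Worked case, q = 0.30, new codes cut by 25%:

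- Control: q* = 1 − 0.7 × 0.9 = 0.37. Share = 0.15 + 0.85(0.0606 × 0.37 + 0.9394 × 0.10) = 0.2489. Events = 0.15 × 0.1064 + 0.85 × 0.0606 × 0.37 = 0.0350. Risk = 0.1407.
- Other arm: q* = 1 − 0.7 × 0.925 = 0.3525. Share = 0.2280. Events = 0.0341. Risk = 0.1496.
- Ratio = 0.1496 / 0.1407 = 1.06, where the truth is 1.00.

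| Cut in new codes | Risk ratio, q = 0.30 | Risk ratio, q = 0.60 |
|---|---|---|
| none | 1.00 | 1.00 |
| 10% | 1.02 | 1.03 |
| 25% | 1.06 | 1.07 |
| 40% | 1.11 | 1.12 |

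A simulation of 2,000,000 patients per scenario on the same assumptions, using event rates per person-year, gave about 1.03, 1.07 and 1.11-1.13. With membership fixed on the randomisation ECG it gave 0.99-1.01. The MI rate within the subgroup rose from 2.2% per year (baseline codes only) to 3.0-4.1%, because patients with events are drawn in.

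**Calculation 2: the protocol's effect, equal in every patient.** Take the control risk as R = 0.069 whatever the baseline code, and a true ratio of 0.845. Let p = 0.05-0.25, q = 0.30-0.60 and n = 0.05-0.15. Here an event leaves a code with chance q, and the background chance nr applies to event-free patients only. Subgroup risk = R[p + (1 − p)q] / {p + (1 − p)[Rq + (1 − R)nr]}, with R multiplied by 0.845 in the treated arm. For example, p = 0.15, q = 0.60, n = 0.15 gives a control risk of 0.069 × 0.66 / 0.304 = 0.150. With r = 0.85 the ratio is 0.911 inside the subgroup and 0.819 outside.

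| r | Ratio inside | Ratio outside |
|---|---|---|
| 1.00 | 0.848-0.882 | 0.840-0.843 |
| 0.85 | 0.866-0.951 | 0.819-0.836 |
| 0.70 | 0.882-1.065 | 0.799-0.830 |

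The gap between the columns is a spurious interaction, since every patient has the same true effect. Over the same grid with no true effect on the endpoint, the inside ratio is exactly 1.00 at r = 1, 1.017-1.109 at r = 0.85 and 1.034-1.245 at r = 0.70.

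**After the fix.** With membership read from the randomisation ECG, the expected ratio is the true one in both strata: 0.845 under the planned effect and 1.00 under none.

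**The case against.** The strongest reply is that the protocol adopts no such rule. It defers the decision to the Steering Committee and then says only that patients could be so classed. That stands, and a reader who infers that the appendix has fixed this subgroup goes further than the text. What remains is that this is the only criterion put before the committee, and its second limb is unsound for a subgroup.

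A second reply is that the sentence may simply list two things for the ECG readers to record: codes at entry, and codes that develop later. The wording allows this. It follows directly on the sentence about subgroup criteria, however, so the other reading is at least as natural, and the text does not separate the two uses.

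Third, a reader might infer that the subgroup effect is bound to be biased. It is not. With no effect on new codes and none on the endpoint, the ratio is exactly 1.00, and the size and direction otherwise depend on rates the protocol does not give. Nor does every infarction leave ST-T codes; the calculations assume 30-60%. ST-T codes are also not the endpoint itself, since silent infarction is read from the Q and QS codes 1.1 and 1.2.

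Fourth, one might extend the point to the vascular-disease subgroup in tertiary objectives 5 and 6. The documents do not support that: the word 'previous' already makes the ECG part a baseline item.

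Finally, the work is exploratory. That is correct and keeps the point small.

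**Conclusion.** The point holds as a conditional one. If the Steering Committee takes up the candidate in Appendix ID as worded, subgroup membership would rest partly on post-randomisation ECGs, and the subgroup ratio and interaction test could mislead. Under the first set of assumptions with no true effect, the spurious ratio is about 1.03 to 1.13 for a 10-40% cut in new codes. Under the protocol's own 0.845 in everyone, the subgroup drifts towards or past 1 as the effect on codes grows. Even with no effect on background codes it shows 0.848-0.882 against 0.840-0.843 outside. All these sizes rest on assumed code rates. The primary and secondary tests, the sample size and the subgroups named in the objectives are unaffected, so this is a minor correction of wording.

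**What to change.** In Appendix ID, remove the words 'or appear' from the sentence on possible ischaemia as far as subgroups are concerned, and state that the ST-T class is defined from the randomisation ECG only. Apply the same rule to the conduction-defect codes 7.1, 7.3 and 7.6 if they are used as a class. Report newly appearing codes by arm as an outcome. Tertiary objectives 5 and 6 need no change.

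The cost is one wording change and a somewhat smaller subgroup. No new data are needed: the randomisation ECG is already taken and sent to the co-ordinating centre, and the ECG core centre already codes tracings blind.
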